5.2.1 Secondary endpoints supporting the secondary objective(s)

- Change from baseline in HEAD-US score for hypertrophic synovium at 6, 12 and 18 months
- Change from baseline in HEAD-US score for cartilage at 6, 12 and 18 months
- Change from baseline in HEAD-US score for bone at 6, 12 and 18 months
- Change from baseline in total HJHS at month 18 (EOS)
- Number and location of target joints at baseline, 6, 12 and 18 months
- Total Annualized bleeding rate (ABR), joint ABR, target joint ABR, traumatic/spontaneous ABR
- Patient-Reported Outcomes Measurement Information System (PROMIS) physical function/activity scores at baseline and 18 months
- PROMIS pain intensity and interference scores at baseline and 18 months
- International Physical Activity Questionnaire - Short Form (IPAQ-SF) scores at baseline and 18 months

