6.1 Overall study design and plan

This is a prospective, low-interventional, single-arm, multicentre study to describe the joint health over an 18-month period of prophylactic treatment with rFVIIIFc or rFIXFc in patients with haemophilia A or haemophilia B in a real-world setting. Approximately 250 patients will be enrolled in the study. Around 80% of the patients are expected to have haemophilia A and around 20% haemophilia B.

Retrospective data from patient medical records will be collected for at least 6 months before enrolment in the study. From enrolment and throughout the study, patients will perform on-site study visits at 6-month intervals. Each patient is expected to actively participate in the study for 18 months (from baseline to end of study [EOS] visit).

Joint health will be assessed with HEAD-US and HJHS scoring. Quality of life and physical activity will be assessed with PROs. Patients will be on prophylactic treatment with rFVIIIFc or rFIXFc according to usual clinical practice and the dosing guide in the respective Summary of Product Characteristics (SmPC). Choice of treatment will not be dictated by the study protocol.

The recruitment period is planned to be approximately 12 months from the timepoint when the first patient is enrolled in the study. Around 60 sites in approximately 11 European countries are expected to participate in the study.

No specific evaluation committees will be utilized for this study, since it is a low-interventional study having no interventions posing more than minimal risk to the patients.

Interim analyses are planned to be performed during the study. The first interim analysis is to be performed once recruitment is completed. The purpose of the first interim analysis is to assess the baseline variability of HEAD-US score results and to share baseline characteristics with the haemophilia community. The second interim analysis is planned to be performed once at least 50% of the patients have completed their 12-month visit and will evaluate the joint health status at that time.

In an optional, exploratory sub-study, data will be collected via the florio HAEMO app. All exploratory endpoints and objectives in the study are related to the exploratory sub-study.

[figure not shown]
The overall study design is described in Figure 1.

Sobi

Eftrenonacog alfa/Alprolix® - Efmorocog alfa/Elocta®

Clinical Study No: Sobi.HAEM89-007

Figure 1 Study Design

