6.5.10.3 Patient-Reported Outcomes

Patient questionnaires will be administered at the baseline and 18 months (EOS), to evaluate and compare changes in patients' perceptions of pain and physical activity/function. PRO questionnaires will be completed by patients or caregivers depending on age, see Table 1 for additional details. When possible, caregivers of paediatric patients less than 8 years old will complete the PRO instruments verbatim based on the patient's responses. Patients and/or caregivers will be encouraged to complete the PROs based on the patient's age at enrolment. It is expected that it will take approximately 8-10 minutes per visit to complete all questionnaires. The PROs are expected to be completed on paper and the paper forms will be considered as the source document for the PRO data. Due to language availability, not all patients may be required to complete all PROs.

Sobi

Eftrenonacog alfa/Alprolix® - Efmoroctocog alfa/Elocta®

Clinical Study No: Sobi.HAEM89-007

Table 1 PRO questionnaires

Instrument	Patients aged ≥6 - <12 years	Patients aged >8 - 17 years	Patients aged ≥18 years
PROMIS Pain intensity 3a			X
PROMIS Paediatric pain intensity 1a		X ²	
PROMIS Parent proxy pain intensity 1a	X ¹		
PROMIS Pain interference short form 6a			X
PROMIS Paediatric pain interference short form 8a		X ²	
PROMIS Parent proxy pain interference	X ¹		
PROMIS Physical function/activity short form 6b			X
PROMIS paediatric physical activity short form 8a		X ²	
PROMIS parent proxy physical activity short form 8a	X ¹		
IPAQ-SF			X ³

Abbreviations: IPAQ-SF: International Physical Activity Questionnaire - Short Form; PRO: patient-reported outcome; PROMIS: Patient-Reported Outcomes Measurement Information System

¹ PRO completed on behalf of the patient by the caregiver as proxy

² PRO completed on behalf of the patient by the caregiver, or by the patient, if possible

³ Age range to be aligned with questionnaire age range

Information on whether questionnaires are completed by the patient or by a caregiver will be collected and accounted for in the statistical analysis.

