The IPAQ-SF is a validated, 7-day recall questionnaire suitable for people between 15-69 years of age to measure current levels of physical activity (30). IPAQ-SF assesses physical activity across domains; leisure-time physical activity, domestic and gardening activities, work-related physical activity and transport-related physical activity. The items are structured to provide separate domain specific scores for walking, moderate-intensity and vigorous-intensity activity within each of the work, transportation, domestic chores and gardening (yard) and leisure-time domains. Scoring of the IPAQ-SF results in a continuous variable in the form of total MET-minutes per week, as well as categorization into high, moderate or low physical activity level. The IPAQ-SF will be administered at baseline and at the yearly visits. It is expected to take approximately 5 minutes to complete.

6.5.11 **Exploratory endpoints - florio HAEMO sub-study**

If a patient has used florio HAEMO (a certified medical device used in routine clinical practice) for at least 3 months and agrees to have data collected from it by providing informed consent, the patient can participate in the florio HAEMO exploratory sub-study.

A questionnaire on the impact of florio HAEMO on patients' sense of protection and their physical activity level will be administered, and data from florio HAEMO on estimated FVIII levels, physical activity levels, bleeds, pain, well-being and rFVIIIFc/rFIXFc dosing will be collected. Data will be retrospectively collected from the 6-month period prior to enrolment, and until EOS.

6.5.11.1 **florio HAEMO patient questionnaire**

All patients who use florio HAEMO to monitor their haemophilia, or their caregivers for patients <12 years of age (Table 2), and who consent to the use of florio HAEMO data in the study, will

Sobi

Eftrenonacog alfa/Alprolix® - Efmorocog alfa/Elocta®

Clinical Study No: Sobi.HAEM89-007

be asked to complete a questionnaire (Appendix 2 and Appendix 3) including questions about their use of florio HAEMO, and if florio HAEMO has an impact on their sense of protection and activity level. The questionnaire will be completed one time during the study and administered once a patient has used florio HAEMO for at least 3 months.

Table 2 florio HAEMO patient questionnaire

Instrument	Patients aged <8 years	Patients aged 8 to <12 years	Patients aged 12 to <18 years	Patients aged ≥18 years

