8.3.4 Analysis related to secondary objectives

A detailed description of the secondary objectives and endpoints are found in section 5.2 of the protocol. The secondary endpoints will be based on both the FAS and the PP set.

HEAD-US scores (hypertrophic synovium, cartilage, bone) and HJHS scores (Sum of joint totals, Global Gait Score, HJHS total score) will be presented using descriptive statistics at each visit. In addition, the change from baseline to each post-baseline visit will also be presented with descriptive statistics and the estimated average change from baseline together with 95% CI.

The number and proportion of patients with target joints as well as the total number of target joints will be analyzed by summary statistics as well as frequency tables for each visit. Target joint locations will be given for each visit in frequency tables.

The ABR for treated bleeds and ABR for all (treated and untreated bleeds) will be derived for the period between baseline and month 6 visit, for the period between month 6 and month 12 visit, for the period between month 12 and month 18, and as well as for the entire 18-month study period. The ABR will also be presented for the retrospective 6 month period. ABR will be presented using summary statistics for all periods and also be presented by type (spontaneous/traumatic/unknown) and location (joint/muscle/unknown). The number and

Sobi

Eftrenonacog alfa/Alprolix® - Efmorocog alfa/Elocta®

Clinical Study No: Sobi.HAEM89-007

percentage of patients who had at least one bleeding episode (overall, circumstance, locations and target joint) over the 18-month prospective period will also be presented as well as the corresponding total number of episodes. The number and proportion of patients with 0 joint bleeds will be presented, as well as the number and proportions with 1, 2 etc. joint bleeds. To justify an estimation of the ABR and to reduce potential misclassification, a patient had to be documented for at least 3 months.

PROMIS and IPAQ-SF scores will be presented at baseline and 18 months graphically and in tabular form with descriptive statistics (mean IPAQ-SF score measured as MET-minutes/week) and change.

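### Physical activity is reported as raw change between two one-week snapshots about half a year out of calendar phase, so uneven enrolment over the year would shift the mean change by season

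*Combined protocol and SAP*

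**What the plan says.** - **Collection.** Section 6.5.10.3: "Patient questionnaires will be administered at the baseline and 18 months (EOS), to evaluate and compare changes". The schedule of events (6.5.1.1) marks PROs at enrolment/baseline and at month 18 only.
- **Endpoint.** Section 5.2.1 lists "International Physical Activity Questionnaire - Short Form (IPAQ-SF) scores at baseline and 18 months".
- **Analysis.** Section 8.3.4: "PROMIS and IPAQ-SF scores will be presented at baseline and 18 months graphically and in tabular form", with descriptive statistics and change. It gives no covariates for these scores. The covariates listed in 8.3.3 are for the HEAD-US model and include no calendar term.
- **Recall and content.** Section 6.5.10.3.2: "The IPAQ-SF is a validated, 7-day recall questionnaire". It covers "leisure-time physical activity, domestic and gardening activities, work-related physical activity and transport-related physical activity". Section 6.5.10.3.1 gives PROMIS the same 7-day recall.
- **Setting.** Section 6.1 expects about 60 sites in about 11 European countries, and adds: "The recruitment period is planned to be approximately 12 months from the timepoint when the first patient is enrolled in the study". Section 6.2 states that there is no control group.
- **A conflicting sentence.** Section 6.5.10.3.2 also says: "The IPAQ-SF will be administered at baseline and at the yearly visits". That implies a month-12 IPAQ-SF, which appears neither in the schedule nor in 5.2.1, 6.5.10.3 or 8.3.4.

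No section mentions season or calendar time.

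**The concern.** A 7-day recall samples one week of the year. For a measure that counts walking, gardening and outdoor leisure, that week matters. Eighteen months is one and a half years, so a patient first asked in July is asked again in about January. All sites are in Europe, so patients enrolled in the same months are shifted in the same direction, and no control group exists to subtract the shift.

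Patients enrolled in summer and in winter offset each other, but only to the extent that enrolment is balanced over the calendar. If more enrol in the warmer half-year, mean activity appears to fall. If more enrol in the colder half, it appears to rise. Because the study is descriptive, the published mean change is itself the result.

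The point applies to IPAQ-SF and to the PROMIS paediatric and parent-proxy physical activity forms.

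**Working it through.** **The plan's own figures.** None concerns activity or season. The only precision figures are the HEAD-US half-widths in Table 3. The key one reproduces (1.96 × 13/√250 = 1.61), but it plays no part below.

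**Step 1: calendar phase of month 18.** Inputs: the -28/+56-day window (6.5.1.1, 6.5.1.5) and a year of 365.25 days.
- Nominal: 1.5 × 365.25 − 365.25 = 182.6 days past the anniversary, exactly half a cycle.
- Early limit: 182.6 − 28 = 154.6 days past the anniversary.
- Late limit: 182.6 + 56 = 238.6 days, which is 365.25 − 238.6 = 126.6 days before the next anniversary.
- A quarter-year is 365.25/4 = 91.3 days, so the same season is never reached.
- Section 6.5.1.2 dates baseline by the HEAD-US examination and lets assessments be split over 28 days. If the PROs came 28 days before the scan, the late limit becomes 266.6 days, still 98.6 days from the anniversary.
- With visits spread evenly over the window and baselines over the year, about 74% fall in the opposite quarter, 26% in an adjacent one and none in the same one.

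**Step 2: one patient.** Assume a seasonal component s(t) = A cos(2πt), with t in years from the seasonal peak.
- Change = s(t + 1.5) − s(t) = −2A cos(2πt). This reaches 2A only for patients enrolled at the peak or trough.
- At the window limits the maximum is 1.94A (−28 days) and 1.77A (+56 days).
- Under even enrolment the seasonal SD of individual changes is 2A/√2 = 1.41A.
- A month-12 comparison would carry 0 on the nominal date and at most 0.48A within ±28 days.

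**Step 3: the cohort mean.**
- Even enrolment over exactly 12 months: 0.
- Fraction p enrolled in the warmer half-year, evenly within each half: cos(2πt) averages 2/π over the warm half and −2/π over the cold half, so the shift is −(2p − 1)(4/π)A.
  - p = 0.6: 0.2 × 1.273 = 0.25A downward.
  - p = 0.7: 0.4 × 1.273 = 0.51A downward.
- Linear ramp-up over 12 months (density 2x): the mean seasonal vector has length 1/π, so the shift is at most 2A/π = 0.64A, with a sign that depends on the start month.

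**Step 4: in percent, for an assumed A of 10% to 20% of mean activity.**

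| Enrolment pattern | Shift | A = 10% | A = 20% |
|---|---|---|---|
| Even, 12 months | 0 | 0 | 0 |
| 60/40 by half-year | 0.25A | 2.5% | 5% |
| 70/30 by half-year | 0.51A | 5.1% | 10.2% |
| Linear ramp-up (worst start month) | up to 0.64A | up to 6.4% | up to 12.7% |

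**Step 5: does a calendar term remove it?** Regress change on an intercept and the sine and cosine of baseline date. A simulation used n = 250, a 70/30 split, A = 0.15 residual SDs and a true change of 0.
- Raw mean: −0.075 (formula: −0.509 × 0.15 = −0.076).
- Model intercept: 0.002.
- Standard error: 0.064 raw against 0.067 from the model, a ratio of 1.05.

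**Step 6: is a half-year split just as good?** Not quite. The equal-weight average of the two halves cancels season only if enrolment timing within one half mirrors the other. Under the linear ramp-up it still leaves up to 0.19A.

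**The case against.** **Recruitment of about 12 months covers one full seasonal cycle, and even enrolment gives no bias.** This stands. Nothing in the documents shows that enrolment will be uneven, and both the splits and A above are assumptions. But the plan does not make enrolment even either: the period is approximate, and staged opening of some 60 sites would produce a ramp-up. Even enrolment over 15 rather than 12 months would still leave up to 0.36A.

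**The effect is modest against sampling error.** In the simulation the 0.075 shift lies inside a 95% half-width of 1.96 × 0.064 = 0.125. Table 1 marks IPAQ-SF for adults only, so its n will be below 250 and the relative bias smaller. The extra spread is slight: under even enrolment the SD rises from 1 to √(1 + 2 × 0.15²) = 1.02. This stands too, and keeps the point small.

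**Other activity data exist.** A month-12 IPAQ-SF would be season-matched, but it appears in one sentence that other sections contradict, and 8.3.4 does not analyse it. The florio HAEMO activity data come from an optional exploratory sub-study.

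**Details are left to a separate SAP.** Section 8.3.1 does say so. But 8.3.4 already names the summary, and that summary leaves the calendar contrast in.

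**Stronger readings that a reader might infer, and that the documents do not support:**
- That the two assessments always fall in opposite seasons. The window allows an adjacent one.
- That shifts between IPAQ activity categories are affected. Section 8.3.4 plans mean MET-minutes per week and change; the categories appear only as a scoring output.
- That adult PROMIS physical function is equally exposed. Section 6.5.10.3.1.3 describes dexterity, mobility and daily living, and nothing suggests that these are seasonal.
- That bleeding rates are compared across opposite half-years. Section 8.3.4 says "The ABR will also be presented for the retrospective 6 month period" but does not set that period against months 0-6, and no seasonality of bleeding is documented.

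**Conclusion.** The point holds as a cheap improvement, not as a flaw that undermines the study. The planned raw change in IPAQ-SF and in the PROMIS paediatric and proxy activity scores contains a near-maximal calendar contrast that nothing in the design or analysis removes. Its effect on the mean is conditional: zero under even 12-month enrolment, about 0.25A at 60/40, 0.51A at 70/30, and up to 0.64A under a linear ramp-up.

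These figures rest on a single annual cosine with the same phase for all patients, and on an amplitude that the documents do not give, so they cannot show that the reported mean will be biased. Nor do the documents treat a change in activity as an effect of prophylaxis: the objective in section 5.2 is to evaluate quality of life, and section 8.3.1 plans no hypothesis testing.

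**What to change.** - **Section 8.3.4 or the SAP.** For IPAQ-SF MET-minutes per week and the PROMIS paediatric and proxy physical activity scores, keep the raw mean change. Beside it, report the mean change from a linear model with an intercept and the sine and cosine of the baseline calendar date. The intercept is the change averaged evenly over the year.
- **One added table.** Show change by enrolment half-year (April-September, October-March), labelled as a descriptive and only approximately equivalent check.
- **IPAQ-SF schedule.** Reconcile the yearly-visits sentence in 6.5.10.3.2 with 5.2.1, the schedule of events, 6.5.10.3 and 8.3.4. If a month-12 IPAQ-SF is collected, report that season-matched change as well.
- **ABR.** Add a note that the retrospective six months and months 6-12 cover nominally the same calendar months. No change to the ABR analysis is needed.

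**Cost.** SAP wording and one table, using dates already recorded, with no new visit or patient burden. The standard error is about 5% larger under a 70/30 split. The model needs baselines in both halves of the year; if enrolment falls almost wholly in one half, the intercept is an extrapolation, and the limitation should simply be stated. Fix the analysis before follow-up data are seen, so that a seasonal explanation is not offered after the fact.

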8.3.5 Analysis related to exploratory objectives

All patients who use florio HAEMO or their caregivers for patients <12 years of age and who consent to the use of florio HAEMO data in the study, will, once they have used florio HAEMO for at least 3 months, be asked to complete a questionnaire with questions about their use of florio HAEMO, how it affects their haemophilia management, and if it has an impact on their sense of protection and activity level. The results from the questionnaire will be summarized using descriptive statistics as appropriate. Data generated from florio HAEMO (treatment adherence scores, estimated FVIII or FIX levels, physical activity levels, dosing, bleeds, pain, well-being) will be analyzed and described in the SAP.

8.3.6 Analysis of safety and tolerability data

8.3.6.1 Adverse events

Reported AEs during the study will be coded using the Medical Dictionary for Regulatory Activities. The incidence of AEs will be summarized in frequency tables by treatment, system organ class, preferred term and maximum severity. Separate tabulations will be performed for serious and non-serious AEs.

8.3.7 Interim analysis

Interim analyses are planned to be performed during the study. The first interim analysis is to be performed once recruitment is completed. The purpose of the first interim analysis is to assess the baseline variability of HEAD-US results and to share baseline characteristics with the haemophilia community. The second interim analysis is planned to be performed once at least 50% of the patients have completed their 12-month visit and will evaluate the joint health status at that time.

8.3.8 Handling of missing data

Methods for handling missing data will be described in the SAP.

Sobi

Eftrenonacog alfa/Alprolix® - Efmorocog alfa/Elocta®Clinical Study No: Sobi.HAEM89-007

9 Data collection, handling and record keeping

9.1 Data standards

Collection of data should be performed in the Clinical data acquisition standards harmonization format, according to the Clinical data interchange standards consortium (CDISC). The standards should be used to the extent possible and/or required for the specific study/project. The minimum requirement of the CDISC standard is to collect all core variables specified as 'Required' in the Study Data Tabulation Model format.

9.2 Case report form

A CRF is required and should be completed for each enrolled patient. In this study a web based, validated electronic data capture (EDC) software tool will be used to collect and process the study data. The management of the EDC system will be based on the model of outsourcing.

The data should be entered by site users into the EDC system on an ongoing basis. In principle, it is recommended to perform data entry within 5 working days from the visit date unless otherwise specified by the site Clinical Trial Agreement. To ensure data quality within EDC, automated edit checks will be built into the EDC system and triggered to correct or verify the input data. Any data changes or modifications within EDC will be automatically tracked by an audit trail detailing date, time and name of the user performing corrections.

Clinical data management will be conducted in accordance with regulatory standards. This applies to data recorded directly in eCRF and to data from other sources stored at secure servers (e.g. IXRS, Laboratory). Additional details regarding data collection and validation procedures will be detailed in a Data Management Plan.

Access to the EDC system is granted and revoked in accordance with regulatory requirements. Only authorized personnel will have access to the EDC system upon completion of the user training.

The investigator will review and approve the eCRF entries for each patient with an electronic signature. The signatures serve to attest that the information contained on the eCRFs is correct. At all times, the investigator has final responsibility for the accuracy and authenticity of all data entered in the eCRF.

The completed original eCRFs are the sole property of Sobi and should not be made available in any form to third parties, except for authorized representatives of appropriate regulatory authorities, without written permission from Sobi.

At the end of the study, a final copy of the database will be stored at the Sponsor. Sobi will ensure that an eCRF copy of trial's final and locked data is provided to the Investigator in a form of a write protected PDF files and that the eCRF copies are an exact copy of the data maintained in the database.

Sobi

Eftrenonacog alfa/Alprolix® - Efmorocog alfa/Elocta®Clinical Study No: Sobi.HAEM89-007

